Adult half-body manikin and a pediatric full-body manikin are necessary; with lung bag inflation and deflation characteristics, palpable carotid pulse, the chest includes spring inside to facilitate chest recoil, and chest compression board, bag-valve-mask-ventilation, chest compression performed on the Charlie simulator to relieve choking. The principles investigator (PI) had a master's degree in critical care nursing, eighteen years of experience between ICUs, lecturers and clinical instructors, valid BLS and ACLS, training of trainers in nursing education, and randomized control trial training. The facilitator must have CPR certifications in BLS and ACLS, enough expertise in education and training, and good communication skills the investigator had a master degree in critical care. Two research assistants supported the

PI in collecting data; one research assistant for the control group and the other for the interventional group.

Post-test

All participants completed the immediate post-test-1 after the interventions. The post-test-2 was conducted by providing the participants with a Google Form Platform link through their phone and email addresses. The post-test after three months evaluates whether the participants' level stayed at the same level or minimized by comparing the mean value between all post-tests. Forty-eight participants in the experimental group completed post-test-2 with a response rate of 94%, and 45 participants in the control group with a response rate of 88%.

Sample Size Estimation

Sample size calculation is performed by using G*POWER software (version 3.1); sample size calculation is summarized and consists of the following steps (1) Select the test family (F-test family), (2) Select the statistical test (Select ANOVA-repeated test, between factors), the preliminary test analysis the researchers used in this study, the rationale for using the Select ANOVA-repeated test between factors due to measure many dependent variables means at different time points. (3) The parameters selected to calculate sample size include one side tail, alpha (α) and equals (0.05)- type one error, Power (P) and equal (0.8), effect size, the number of groups is two (each group = $n/2$) n = the estimated sample size, number of measurements were four measurements (Pre-test, Post-test immediately, Post-test after two months, and Post-test after three months).

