DEVELOPMENT, VALIDATION, AND
EVALUATION OF THE EFFECTIVENESS OF
SIMULATION IN BASIC LIFE SUPPORT TRAINING
(SBLST) ON NEWLY EMPLOYED NURSES IN
GOVERNMENTAL JORDANIAN HOSPITALS

Statistical Analysis Plan

Last update On 20-4-2023

Malaysian Human subjects protection review board date: 20-4-2023

Statistical Analysis Plan

Introduction

The data will be collected through the Google Forms platform, and the researchers will extract the data responses from Google Forms as an Excel sheet (Microsoft Office 2016); all the quantitative data will be coded and transferred to IBM SPSS version 27; the data will be analyzed by using (1) descriptive and (2) inferential statistic.

1. Descriptive Statistics

The descriptive statistic will illustrate the homogeneity and characteristics of NEN in the control and experimental group, including the number and percentage of participants for each group. Also, it will be used to describe statistics for participants' knowledge, practice and confidence level mean percentage in the pre-test and post-test scores.

2. Inferential Statistics

A. Independent T-test

Independent T-test will be used to identify the homogeneity or heterogeneity between pre-tests and post-tests in the control and experimental groups in all dependent variables by interpreting the *P*-value and comparing means (SD). The researchers plan to use independent T-tests despite the normality assumption not being fulfilled depending on the central limit theorem, which states that if samples are more than 30 participants in each group, the researcher can use mean and SD.

B. Repeated Measures-ANOVA

The researchers will use "Repeated Measurement ANOVA" for inferential statistics of the mean of the dependent variables between the interventional and comparator groups in all pre-test and post-tests. Finally, the researchers compared the

*

“Mean,” “Standard Deviation,” and significant level (*P*-value) between tests to explore the effectiveness of the intervention SBLST.

In this step of the analysis, the researchers want to estimate a good idea about the outcomes and how SBLST is considered a good intervention or not after comparing the knowledge score, practice score, and confidence level in both interventional and control groups. The researchers selected a *P*-value < 0.05 for statistical analysis significant to accept the alternative hypothesis or reject the null hypothesis.

C. Effect Size (Cohen’s Score)

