The researchers will calculate the effect size between pre-test and post-test-2 in each group and identify the most effective treatment method that increases knowledge, practice and confidence score. Effect size reflects the SBLST's effectiveness if it produces a small, moderate or large effect. The researchers plan to use Cohen’s formula (d) to calculate the effect size; effect size assists the researcher in interpreting the effectiveness of the SBLST before and after intervention and also interpret the two intervention in two groups after the intervention, according to the following category (<0.2), small effect; (0.2-0.8), moderate effect, (>0.8), large effect; and finally more than 0.9, very large effect (La Cerra et al., 2019).

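### On its natural reading, SAP 2.C picks the most effective method by comparing two within-arm pre-post Cohen's ds, with no named SD, no interval on their difference and no condition on the 2.B result

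*SAP*

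**What the plan says.** SAP 2.C (Effect Size) plans to "calculate the effect size between pre-test and post-test-2 in each group and identify the most effective treatment method" for knowledge, practice and confidence. It names Cohen's d but not the SD that divides the change, and it plans no confidence interval for either d or for their difference.

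The same paragraph gives d two supporting uses. One is within-arm: "effect size assists the researcher in interpreting the effectiveness of the SBLST before and after intervention". The other is between arms: d will also "interpret the two intervention in two groups after the intervention". The second has no time point, SD or interval, and is not made the basis for naming the better method. The ds are then labelled "according to the following category (<0.2), small effect; (0.2-0.8), moderate effect, (>0.8), large effect; and finally more than 0.9, very large effect".

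SAP 2.B (Repeated Measures-ANOVA) compares the arms across the tests and holds the only decision criterion, P < 0.05, "for statistical analysis significant to accept the alternative hypothesis or reject the null hypothesis". It frames the question as whether "SBLST is considered a good intervention or not after comparing the knowledge score, practice score, and confidence level in both interventional and control groups". No sentence in 2.C refers to that result.

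**The concern.** A pre-post d in one arm measures that arm's change: learning, retesting and the intervention together. The comparison between SBLST and the brochure lies in the difference between arms, and that difference has its own sampling error. Two within-arm ds can differ visibly by chance when the true gains are equal. They can also differ because the arms have different SDs or because one choice of SD was used rather than another.

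A report could therefore follow 2.C as written and call SBLST the most effective method for an outcome on which the 2.B comparison shows no difference. The lowest band adds a small problem of its own: taken literally, it has no lower limit, so a d of zero, or a negative d, would be labelled a small effect.

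**Working it through.** The SAP gives no d, SD or pre/post correlation, so there is no planned figure in 2.C to reproduce. What follows shows how far two within-arm ds can be relied on at this trial's size.

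**Inputs from the documents**
- Completers at post-test-2 (Protocol, Post-test): "Forty-eight participants in the experimental group completed post-test-2", and "45 participants in the control group with a response rate of 88"%. Check against 51 per arm: 48/51 = 94%, 45/51 = 88%.
- Planning data (Protocol, Sample Size Estimation): control 25.03 ± 3.04 (n = 28), intervention 26.64 ± 2.64 (n = 29).
- Bands cut at 0.2, 0.8 and 0.9 (SAP 2.C).

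**Assumptions**
- Pre/post correlation r from 0.3 to 0.7, normal scores, and hospitals ignored unless stated.
- d = mean change / √((var_pre + var_post)/2).
- The between-arm test is a t-test on change, a two-time-point stand-in for 2.B.

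**1. Sampling error of the difference, both true gains zero**
- SD(d₁ − d₀) ≈ √(2(1 − r)(1/48 + 1/45)), with 1/48 + 1/45 = 0.0431.
- r = 0.3: √(1.4 × 0.0431) = 0.246. r = 0.7: √(0.6 × 0.0431) = 0.161.
- Simulation over equal true gains of 0 to 1 SD gives 0.163 to 0.273. Multiplied by 1.96, the 95% interval is about ±0.32 to ±0.54.

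**2. Equal true gains of 0 to 1 SD (simulation)**

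| Event | Share of trials |
|---|---|
| SBLST has the larger d | about 50% |
| The ds differ by more than 0.2, either direction | about 21-46% |
| SBLST leads by more than 0.2 and the between-arm test is non-significant | about 8-20% |

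The 0.2 gap is illustrative; the SAP sets no threshold.

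**3. Band labels, equal true gains.** The arms fall in different bands in about 62% of trials at a true gain of 0.8, which lies on a cut-off. At 0.5 the figure is 4-18%.

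**4. A real effect of the planning size**
- Pooled SD = √((27 × 3.04² + 28 × 2.64²)/55) = 2.84, so d = 1.61/2.84 = 0.57.
- With gains of 1.07 and 0.5 SD (the control gain is assumed), SBLST ranks first in 98-99.9% of trials.

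**5. The unnamed SD**
- d on the change SD = d on the average SD × 1/√(2(1 − r)), which is 0.85 at r = 0.3 and 1.29 at r = 0.7.
- If r differs between arms, the ranking can reverse. Raw-SD ds of 0.70 (r = 0.4) and 0.60 (r = 0.7) become 0.70/√1.2 = 0.64 and 0.60/√0.6 = 0.77.

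**6. Unequal arm SDs, same raw gain**
- If the planning SDs applied throughout, SBLST's d would be 3.04/2.64 = 1.15 times the control d.
- If baseline SDs were equal at 2.84, the average SDs would be √((2.84² + 3.04²)/2) = 2.94 and √((2.84² + 2.64²)/2) = 2.74, a ratio of 1.07.

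**The case against.** The strongest reply is that 2.C is secondary. Sections 2.A and 2.B already compare the arms, 2.B holds the only decision criterion, and 2.C says only that d assists interpretation. Testing first and describing size afterwards is the usual order. The key sentence joins two actions with *and*; it does not say that the larger within-arm d wins. The paragraph also mentions a between-group reading of d.

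Most of this stands, and it limits the point. A reader might infer that the trial judges effectiveness only on within-arm change, or that the SAP fixes a rule of ranking by d. The documents support neither: between-group tests are planned, and the ranking is the natural reading rather than a stated rule. What remains is that the only statistic in the sentence that names the best method is a d computed in each group, and nothing makes that statement conditional on 2.B.

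The percentages also depend on chosen conditions. The 0.2 gap is not the SAP's, and the high band disagreement arises at a cut-off. Under the planning effect the ranking is nearly always right. SBLST then ranks first without a significant between-arm test in 6-36% of trials using the change-score t-test, and in about 3-18% using a pre-test-adjusted test. Those are missed real effects, not false claims of superiority.

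The planning SDs are post-test SDs from a small earlier study, so the 15% inflation is an upper case. The remark about zero or negative d is minor, since bands are often read as magnitudes.

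**Conclusion.** The point holds for the most-effective statement and the effect labels in 2.C, and no further. When the two methods are equally good, the larger within-arm d falls to SBLST about half the time. In about 8-20% of trials SBLST leads by more than 0.2 with a non-significant between-arm test of change. A difference in ds carries a 95% interval of about ±0.32 to ±0.54. The choice of SD rescales d by 0.85 to 1.29, and unequal arm SDs could inflate SBLST's d by about 7-15%.

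These sizes rest on 48 and 45 completers, r of 0.3 to 0.7, true gains of 0 to 1 SD and no clustering by hospital. They should not be read as false-positive rates for the trial, because the 2.A and 2.B tests are not affected by this defect. Importance is minor to moderate. The change is still worth making because it is cheap and the statement is one that readers will quote.

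**What to change.** Amend SAP 2.C as follows.

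- Base any statement about the most effective method on the between-arm difference at post-test-2, adjusted for the pre-test already collected and standardised by the pooled baseline SD. Give a 95% CI that handles allocation by hospital in the same way as the main analysis.
- Make the statement for an outcome only if the 2.B between-group comparison for that outcome supports it. Section 2.B does not name the group-by-time term, so say which comparison counts.
- Label the within-arm ds descriptive, name their SD, and do not use them to rank the arms.
- Do not call a d at or below zero an effect.

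**Cost.** SAP wording and one output line per outcome, from data already collected. The reported effect will probably be smaller than a pre-post d.

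Ignoring hospitals, the interval is 1.96 × √(1/48 + 1/45) = ±0.41 SD unadjusted. Multiplied by √(1 − r²), it is ±0.29 (r = 0.7) to ±0.39 (r = 0.3).

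With clustering, assume an ICC of 0.01 to 0.10 and equal hospital sizes within each arm (48/2 = 24 and 45/3 = 15). Then SE = √((ICC + (1 − ICC)/24)/2 + (ICC + (1 − ICC)/15)/3) = 0.226 to 0.349. Multiplied by 3.18 (t on 3 df), this is ±0.72 to ±1.11 SD. After adjustment it runs from 0.72 × 0.714 = ±0.51 (ICC 0.01, r = 0.7) to 1.11 × 0.954 = ±1.06 (ICC 0.10, r = 0.3).

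A reader might infer that an observed difference of 0.57 SD could never exclude zero once clustering is allowed for. At the favourable end (±0.51) it would; over most of the range it would not. That width comes from allocating five hospitals, not from this change.

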Effect Size (ES) = 0.26, automatically calculated by G*Power software, depending on the sample size of the previous study, the effect size is calculated, the

Control group's post-test result $M \pm SD$ was equal (25.03 ± 3.04) with a sample size of 28 participants, and the interventional group (26.64 ± 2.64) with sample size 29 participants. The sample size is 72 participants; because the research study continued for three months, we added a 10% drop rate for each month, so the drop rate is 30%. Final sample size estimation including drop rate ($n \setminus (1 - \text{dropout rate}) = 72 / (1 - 0.30) = 102$ participants, the intervention group arm is 51 participants, and The largest sample size was obtained from the interventional group, more than the Control Group and the Control group arm 51 participants.

Simple Random Sampling of the Participants

After obtaining ethical approval and permission to conduct the study from the Ministry of Health in Jordan, approval letter (Education/Info\ 15177) and ethical approval letter (MOH/REC/2022/340), The researchers started the formal face-to-face visits to arrange with the nursing director and a continuous education office in the selected hospitals about the study objective and how the study would proceed; The researchers received the activation letter to initiate the study and prepared the list of the available participants who met the study's eligibility criteria. The number of participants depends on the availability of newly employed nurses in the institution who meet the inclusion criteria. The researchers randomly selected the participants from the participants' list by randomly sampling from newly employed nurses in each hospital for interventional and control groups.

. The response of the control group hospitals was as the following; the nursing director and continuous education in AL-Zarqa Governmental Hospital responded by providing all the information about participants and selecting a time and day to perform the Pre-test, standard treatment and the immediate post-test. Prince Hamzah Hospital and AL-Basheer Hospital gave the researcher the names of departments in the

hospital, including those with NEN, and we visited these departments to select the available NEN randomly and performed Pre-test, standard treatment, and immediate post-test in their departments.

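### SAP 2.C grades Cohen's d on a scale with no negligible grade and no sign convention, so a d of zero is labelled a small effect of SBLST (minor; wording fix)

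*SAP*

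**What the plan says.** SAP section 2.C (Effect Size) names the metric: "The researchers plan to use Cohen’s formula (d) to calculate the effect size". It applies d to two contrasts. The first is within each arm: "The researchers will calculate the effect size between pre-test and post-test-2 in each group". The second is between the arms after treatment, where d is to "also interpret the two intervention in two groups after the intervention".

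The section then says what the number is for: "Effect size reflects the SBLST's effectiveness if it produces a small, moderate or large effect". The grading scale is "<0.2), small effect; (0.2-0.8), moderate effect, (>0.8), large effect; and finally more than 0.9, very large effect", attributed to a cited paper.

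The section does not give a lower limit for the first band, a grade for no or negligible effect, a rule on the sign of d, the SD to be used, or a confidence interval for d.

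SAP section 2.B (Repeated Measures-ANOVA) has its own criterion: "The researchers selected a *P*-value < 0.05 for statistical analysis significant". It compares means, SDs and P-values to explore whether SBLST works. Section 2.C does not make its label depend on that result.

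**The concern.** Every grade on the scale asserts an effect. A scale meant to say how effective SBLST is should be able to say that it made no appreciable difference, and this one cannot. Because the first band is open below, it takes in zero and, if d is signed, all negative values.

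What is at stake is reporting. The label will be attached to knowledge, practice and confidence, both within arms and between arms. These bands are the only criterion for magnitude in either document. A thesis or paper that follows the SAP to the letter could describe a non-significant or null difference as a small effect of SBLST and be within its plan.

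**Working it through.** **The plan's own effect-size figure.** The bands carry no computed value. The only effect size in the documents is in the Protocol, Sample Size Estimation: "Effect Size (ES) = 0.26, automatically calculated by G*Power software". The control result behind it is "25.03 ± 3.04) with a sample size of 28 participants", and the intervention result is 26.64 ± 2.64 with n = 29.

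- Using the control SD, f = (26.64 − 25.03) / (2 × 3.04) = 1.61 / 6.08 = 0.265, which matches the stated 0.26.
- With four measurements, alpha 0.05, power 0.8 and an assumed correlation of 0.5 (the Protocol gives none), this f returns the stated 72 participants.
- The 0.26 is therefore Cohen's f and should not be read against the d bands. The same data give d = 1.61 / 3.04 = 0.53 with the control SD, or 1.61 / 2.84 = 0.57 with the pooled SD. Both are *moderate* in the SAP.

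The sample size does not use the bands, so nothing below affects it.

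**Literal classification.** The four inequalities are applied to a range of d, first signed and then as an absolute value, since the SAP does not say which is meant. For the between-arm contrast, positive is taken to favour SBLST. The last column uses the example bands given under the fix.

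| d | SAP label, d signed | SAP label, absolute value | Label after the fix |
|---|---|---|---|
| −1.0 | small | large and very large | large, favours brochure |
| −0.5 | small | moderate | moderate, favours brochure |
| 0 | small | small | negligible/no effect |
| 0.1 | small | small | negligible/no effect |
| 0.25 | moderate | moderate | small |
| 0.57 | moderate | moderate | moderate |
| 0.85 | large | large | large |
| 1.2 | large and very large | large and very large | large |

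The rows for 0 and 0.1 give the same wrong label under either convention. The negative rows go wrong under both, but differently: signed, a result against SBLST is called small whatever its size; as an absolute value, its size is kept and its direction is lost.

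**How often this matters if the arms are truly equal.** Inputs are 48 and 45 completers at post-test-2 (Protocol, Post-test), with participants treated as independent and scores as normal.

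- √(48 × 45 / 93) = 4.82, so d = 0.2 corresponds to t = 0.2 × 4.82 = 0.964 on 91 degrees of freedom.
- P(d < 0.2) = 0.831.
- By symmetry, P(|d| < 0.2) = 2 × 0.831 − 1 = 0.66.
- With 51 per arm, P(d < 0.2) = 0.843 and P(|d| < 0.2) = 0.69.

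So in about two thirds of null trials the between-arm estimate would be called a small effect where a negligible grade is the apt one. Allocation was by hospital. Any clustering would spread d more widely and lower this share.

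**The top of the scale.** Read as written, any d above 0.9 satisfies both of the last two definitions, and *large* alone applies only from above 0.8 up to 0.9.

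**The case against.** The strongest reply is that section 2.C is descriptive and section 2.B guards the inference. That is largely right, and it limits the point in several ways.

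- **A reader might infer that a null trial becomes a positive conclusion.** The documents do not support this. SAP 2.B judges SBLST on means, SDs and P < 0.05, so a null trial would also report a non-significant P-value and arm means that show direction. What stands is that 2.C does not link its label to that result.
- **A reader might infer that the plan can never favour the brochure.** It can. Section 2.C computes d separately in each arm in order to pick out the more effective method, and a larger d in the brochure arm would name the brochure. What is missing is a grade for that direction in the direct between-arm comparison.
- **A reader might infer that every negative d is called small.** That holds only if d is signed, which the SAP does not state. The label at zero is wrong under either convention.
- **The overlap above 0.9 has a natural reading.** The last band is introduced as a final tier and can be taken to supersede *large*. Both labels point the same way, so no conclusion turns on it.
- **Chance results above 0.2 are not a fault of these bands.** Any scale with a cut at 0.2 would give them a label. They are a reason to print an interval with d.
- **The bands come from a cited source.** That source was not available, so agreement with it was not checked. The gap is in the SAP's own wording in either case. How wide *moderate* should be is a matter of preference and is not counted as an error here.

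**Conclusion.** The point holds as a minor one. As written, SAP 2.C has no grade below *small effect*, so d = 0 is labelled an effect of SBLST, and a between-arm result favouring the brochure is either called small or stripped of its direction. The zero case needs no assumption beyond the plain wording; the negative case depends on the unstated sign convention. If the arms were truly equal, roughly 66% to 69% of between-arm estimates would be affected, assuming independent participants and normal scores. The uncapped *large* band is a lesser drafting fault.

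The consequence is confined to labelling and reporting. The hypothesis tests, alpha, sample size and power are untouched, and the P-values and arm means from 2.B would let a careful reader see through a wrong label.

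**What to change.** In SAP 2.C:

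1. State that d is signed. Between arms, positive favours SBLST; within an arm, positive means improvement from pre-test.
2. Relabel |d| < 0.2 as negligible/no effect.
3. Make the higher bands mutually exclusive on |d|, with the direction stated, for example 0.2 to <0.5 small, 0.5 to <0.8 moderate, 0.8 or more large. Once the lowest band becomes negligible, *small* needs a range of its own. The exact cuts are the authors' choice, provided they do not overlap.
4. Report each label only with the 95% interval of d and the corresponding 2.B test result.

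The Protocol already reports post-test-2 completion, so this should be recorded as a dated change. The cost is SAP wording only. Some results will earn a less favourable label (d = 0.1 moves from small to negligible, d = 0.25 from moderate to small).
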